### Version History:

Version Number	Date	Comment
1.0 (Original)	06 November 2014	Initial Release
2.0	08 September 2015	Incorporating Global Amendment 1
2.1 - Brazil	16 September 2015	Incorporating Brazil-Specific Amendment
3.1 - Brazil	20 January 2017	Incorporating Global Amendment 2

## SYNOPSIS

Name of Sponsor/Company: Alnylam Pharmaceuticals, Inc
Name of Investigational Product: Patisiran
Title of Study: A Multicenter, Open-Label, Extension Study to Evaluate the Long-term Safety and Efficacy of Patisiran in Patients with Familial Amyloidotic Polyneuropathy Who Have Completed a Prior Clinical Study with Patisiran
Study Centers: This study will be conducted at multiple sites worldwide that have enrolled patients in a previous patisiran study.
Objectives: To assess the safety and efficacy of long-term dosing with patisiran in transthyretin-mediated amyloidosis (ATTR) patients with familial amyloidotic polyneuropathy (FAP).
Methodology: This is a multicenter, multinational, open-label extension study to evaluate the long-term safety and efficacy of patisiran in patients with FAP who have previously completed a patisiran study. Consented eligible patients will enroll in this study and receive 0.3 mg/kg patisiran intravenously (IV) once every 21 ( $\pm$ 3) days for the duration of the study. In order to maintain the every 21-day dosing schedule from the parent study, patients are expected to have their first visit (Day 0) in this study 3 weeks after their last dose visit in the parent study. However, if necessary, a patient may initiate dosing in this study up to 45 days from the time of the last dose in the parent study. Exceptions to this timing may be allowed for medical or regulatory considerations only after consultation with the Medical Monitor. The last testing visit in the parent study will serve as the baseline for this study, unless more than 45 days have elapsed, in which case the baseline tests will need to be repeated on Day 0. Eligibility for this study will be confirmed before administration of the first dose on Day 0. After the Day 0 visit, patients should return to the site for patisiran dosing once every 21 days. Patients will also have visits at the clinical site at approximately 12, 26 and 52 weeks, and yearly thereafter. A complete set of efficacy assessments will be done at 52 weeks, followed by more limited efficacy assessments yearly thereafter. In order to decrease the variability in the efficacy assessment testing at the 52-week visit, there will be a limited number of sites within any one territory that conduct these efficacy assessments (referred to as “Central Assessment Sites [CAS]”); these sites can also dose and manage patients. There will also be sites that can dose and manage the patients (“Patient Care Sites [PCS]”), while sending the patients to the nearest CAS for their 52-week efficacy assessments. Every effort should be made for the patient to return to the same CAS center that the patient went to in the parent study. Yearly efficacy assessments after the 52-week visit may be done at a PCS. Safety will be assessed throughout the study. Patients will return to the clinical site for safety evaluations 12, 26 and 52 weeks during the first year and yearly thereafter. Patients will be continually assessed throughout the study for adverse events (AEs). Unscheduled visits for study assessments may occur if deemed necessary by the study personnel.

**Number of patients (planned):**

All patients who have previously completed a patisiran study may be enrolled if they meet the eligibility criteria for this study.

**Diagnosis and eligibility criteria:**

To be enrolled in the study, patients must meet the following criteria before administration of patisiran on Day 0:

1. Have completed a patisiran study (ie, completed the last efficacy visit in the parent study) and, in the opinion of the investigator, tolerated study drug
2. Be considered fit for the study by the Investigator
3. Have aspartate transaminase (AST) and alanine transaminase (ALT) levels  $\leq 2.5 \times$  the upper limit of normal (ULN), international normalized ratio (INR)  $\leq 2.0$  (patients on anticoagulant therapy with an INR of  $\leq 3.5$  will be allowed)
4. Have a total bilirubin within normal limits. A patient with total bilirubin  $\leq 2 \times$  ULN is eligible if the elevation is secondary to documented Gilbert's syndrome (elevation of unconjugated bilirubin with normal conjugated bilirubin) and the patient has ALT and AST levels within normal ranges.
5. Have a serum creatinine  $\leq 2 \times$  ULN
6. Women of child-bearing potential must have a negative pregnancy test, cannot be breastfeeding, and must be using 2 highly effective methods of contraception prior to dosing in this study and agree to use 2 highly effective methods of contraception throughout study participation and for 75 days after last dose of patisiran in this study.
7. Males with partners of child-bearing potential must agree to use 1 barrier method (eg, condom) and 1 additional method (eg, spermicide) of contraception throughout study participation and for 75 days after the last dose of patisiran in this study; males must also abstain from sperm donation after the first dose of patisiran through study participation and for 75 days after last dose of patisiran in this study
8. Be willing and able to comply with the protocol-required visit schedule and visit requirements and provide written informed consent

A patient will be excluded if they meet any of the following criteria before dosing on Day 0:

1. Has an active infection requiring systemic antiviral or antimicrobial therapy that will not be completed before the first dose of patisiran administration
2. Has poorly controlled diabetes mellitus
3. Has uncontrolled cardiac arrhythmia or unstable angina
4. Is currently taking tafamidis, diflunisal, doxycycline, or tauroursodeoxycholic acid (TUDCA), unless previously allowed per the parent study
5. Is unable to take the required premedications, unless modifications to the premedication regimen were previously allowed per the parent study
6. Is under legal protection (defined as "any person who becomes incapable of protecting his/her interests due to a medically diagnosed impairment of his/her mental faculties that may limit or prevent the expression of his will"), decided by a court

**Investigational product, dosage and mode of administration:**

Patisiran (comprising a small interfering ribonucleic acid [siRNA] targeting mutant and wild type transthyretin [TTR] messenger RNA [mRNA], in a lipid nanoparticle formulation for IV administration), 0.3 mg/kg once every 21 ( $\pm$ 3) days administered as an IV infusion over 70 minutes (approximately 1 mL/minute for the first 15 minutes followed by approximately 3 mL/minute for the remainder of the infusion) by a controlled infusion device.

Patients will receive the following premedications at least 60 minutes before the start of the patisiran infusion:

- Intravenous dexamethasone (10 mg) or equivalent
- Oral paracetamol/acetaminophen (500 mg) or equivalent
- Intravenous H2 blocker (ranitidine 50 mg, famotidine 20 mg, or equivalent other H2 blocker dose)
- Intravenous H1 blocker: diphenhydramine 50 mg (or equivalent other IV H1 blocker available at the study site). Hydroxyzine 25 mg per os (PO, orally) or fexofenadine 30 mg or 60 mg PO or cetirizine 10 mg PO may be substituted for any patient who does not tolerate IV diphenhydramine or other IV H1 blocker.

**Duration of treatment:**

The duration of the study has been determined to allow the collection of long-term safety, tolerability and efficacy data of patisiran in patients with FAP who have completed a prior study with patisiran. The estimated duration of the study is 5 years.

**Reference therapy, dosage and mode of administration:**

Not applicable.

**Criteria for evaluation:**

**Efficacy:**

The efficacy of patisiran will be assessed by the following evaluations:

- Neurological impairment assessed using the Neuropathy Impairment Score (NIS), Modified NIS (mNIS +7) composite score, and NIS+7
- Patient-reported quality of life (QOL) using the Norfolk Quality of Life-Diabetic Neuropathy (QOL-DN) and the EuroQOL (EQ-5D) questionnaires
- Disability reported by patients using the Rasch-built Overall Disability Scale (R-ODS)
- Autonomic symptoms assessed using the Composite Autonomic Symptom Score (COMPASS 31)
- Motor function assessments, including NIS-Weakness (NIS-W), timed 10-meter walk test, and grip strength test
- Polyneuropathy disability (PND) score and FAP stage
- Nutritional status using modified body mass index (mBMI)
- Pathologic evaluation of sensory and autonomic innervation evaluated by intraepidermal nerve fiber density (IENFD) analysis and quantitation of dermal sweat gland nerve fibers (SGNFD) via tandem 3 mm skin punch biopsies taken from the leg (only for patients having this assessment in the parent study)
- Cardiac structure and function through echocardiograms and serum levels of terminal prohormone of B-type natriuretic peptide (NT-proBNP) and troponin I

- New York Heart Association (NYHA) classification of heart failure
- Serum TTR
- Vitamin A
- Thyroid stimulating hormone
- Disease burden and healthcare utilization assessed using a patient-reported pharmacoconomics questionnaire

**Safety:**

Safety assessments will include monitoring for AEs (including serious AEs [SAEs]); clinical laboratory tests, including hematology, clinical chemistry, urinalysis, and pregnancy testing; measurement of anti-drug antibodies (if clinically indicated); vital signs; physical examinations; ophthalmology examinations; and assessment of suicidal ideation and behavior.

**Statistical methods:**

This is an open-label extension study enrolling patients who have previously completed a patisiran study; the size of the study is not determined via power analysis of particular hypotheses tests.

Associations between pharmacodynamic and efficacy data will be explored via correlation.

Descriptive statistics will be provided for clinical efficacy data, clinical laboratory data, vital signs data, and ECG interval data, presented as both actual values and changes from baseline relative to each on-study evaluation. Laboratory shift tables from baseline to worst values will be presented.

**Table 1 Schedule of Assessments**

	Day 0 Visit	12 Week Visit	26 Week Visit	52 Week Visit	Annual Visit	End of Study	Early Withdrawal Visit
	Window ≤45 Days from Last Dose a	±4 Weeks	±4 Weeks	±4 Weeks	±6 Weeks	4 (+1) Weeks from Last Dose	4 (+1) Weeks from Last Dose
Procedure							
Informed Consent	X						
Inclusion/Exclusion Criteria	X						
Medical History	X b						
Demographics	X c						
Physical Examination	X d			X	X	X o	X o
Weight	X Prior to Each Dose					X o	X o
mBMI e	X d			X	X	X o	X o
Height	X c						
FAP Stage and PND Score	X d			X	X	X o	X o
Karnofsky Performance Status	X						
NYHA Classification	X			X			[X] f
Vital Signs g	X Prior to Each Dose						
Safety Laboratory Assessments h	X d	X	X	X	X	X	X
INR	X						
Pregnancy Test	X i	X i (Prior to each dose)				X	X
C-SSRS Questionnaire			X	X	X	X	X

	Day 0 Visit	12 Week Visit	26 Week Visit	52 Week Visit	Annual Visit	End of Study	Early Withdrawal Visit
	Window ≤45 Days from Last Dose a	±4 Weeks	±4 Weeks	±4 Weeks	±6 Weeks	4 (+1) Weeks from Last Dose	4 (+1) Weeks from Last Dose
Procedure							
TTR Protein (ELISA)	X d		X	X	X	X	X
TSH and Vitamin A				X	X	X o	X o
Blood Sample for Long-term Storage	X	X	X	X	X	X	X
mNIS+7 j	X d			X			[X] f
NIS+7 k	X d			X			[X] f
NIS only					X l	X m	X m
Grip Strength Test n	X d			X			[X] f
10-Meter Walk Test p	X d			X			[X] f
Ophthalmology Examination q	X d			X	X	X o	X o
Skin Punch Biopsy (IENFD and SGNFD) r				X	X	X o	X o
Pharmacoeconomics Questionnaire	X			X	X	X o	X o
Norfolk QOL-DN s	X d			X	X	X o	X o
COMPASS 31 Questionnaire	X d			X			[X] f
R-ODS Disability	X d			X			[X] f
EQ-5D QOL	X d			X	X	X o	X o
Echocardiogram	X d,t			X			[X] f
Troponin I and NT-proBNP	X d			X			[X] f
Anti-Drug Antibody Testing u			X	X	X	X	X
Premedication / Patisiran Administration v	X y	X					

	Day 0 Visit	12 Week Visit	26 Week Visit	52 Week Visit	Annual Visit	End of Study	Early Withdrawal Visit
Window	≤45 Days from Last Dose a	±4 Weeks	±4 Weeks	±4 Weeks	±6 Weeks	4 (+1) Weeks from Last Dose	4 (+1) Weeks from Last Dose
Procedure							
Adverse Events	X b Continuous Monitoring						
Concomitant Medications	X b Continuous Monitoring						

**Table 1 Footnotes:**

Abbreviations: C-SSRS = Columbia-Suicide Severity Rating Scale; COMPASS 31 = Composite Autonomic Symptom Score; ELISA = enzyme linked immunosorbent assay; EQ-5D QOL = EuroQOL; FAP = familial amyloidotic polyneuropathy; IENFD = intraepidermal nerve fiber density; mBMI = modified body mass index; mNIS = Modified Neuropathy Impairment Score; MR = magnetic resonance; NIS = Neuropathy Impairment Score; NT-proBNP = N-terminal prohormone of B-type natriuretic peptide; NYHA = New York Heart Association; PND = polyneuropathy disability; QOL-DN = Quality of Life-Diabetic Neuropathy; R-ODS = Rasch-built Overall Disability Scale; SGNFD = sweat gland nerve fiber density; TSH = thyroid stimulating hormone; TTR = transthyretin

a Every effort should be made to perform Day 0 visit 3 weeks (±3 days) from the last dose of study drug in the parent study. However, the Day 0 visit may occur within 45 days after the last dose in the parent study. Exceptions may be made for medical or regulatory considerations only after consultation with the Medical Monitor.

b Medical history includes TTR genotype. Ongoing AEs from the parent study will be captured as Medical History on the case report form (CRF). Similarly concomitant medications that continue from the parent study will be entered into the database.

c Assessment does not need to be repeated. Information will be obtained from parent study.

d Assessment/procedure does not need to be repeated if performed during the parent study within 45 days of first dose in this study.

e mBMI will be calculated within the clinical database; this calculation does not need to be performed at the study center.

f Assessment/procedure required only if patient withdraws before the 52-week visit.

g Vital signs include blood pressure, heart rate, body temperature, and respiratory rate. Collected supine using an automated instrument after patient rests for 10 minutes. Must be performed pre-dose.

h Includes serum chemistry, hematology, and urinalysis. Refer to Section 9.1.5 for specific laboratory assessments.

A urine-based pregnancy test will be performed on all females of child-bearing potential prior to dosing at all visits. In cases where a positive urine pregnancy test result is observed, a serum pregnancy test will be administered and the dose will be held. **No dose will be administered until a negative pregnancy test is observed.** Pregnancy test on the Day 0 Visit does not need to be repeated if the patient had a negative pregnancy test (urine or serum) within 14 days of the first dose.

- j The mNIS+7 consists of the modified NIS tool (weakness and reflexes), nerve conduction studies (NCS) 5 attributes ( $\Sigma 5$ ), quantitative sensory testing (QST) by body surface area including touch pressure (TP) and heat pain (HP), and postural blood pressure. Two assessments of the mNIS+7 will be performed on separate days (1 assessment on each day). The second (repeat) assessment must be conducted at least 24 hours (approximately) but not more than 7 days after the first assessment. Each site will make every effort to have these assessments at the Week 52 visit performed by the same study personnel who performed the assessments for the patient in the patisiran study in which they were previously enrolled.
- k The NIS+7 consists of the NIS tool (weakness, sensation, and reflexes), NCS  $\Sigma 5$ , vibration detection threshold (VDT), and heart rate response to deep breathing (HRdB). Two assessments of the NIS+7 will be performed on separate days (1 assessment on each day). The second (repeat) assessment must be conducted at least 24 hours (approximately) but not more than 7 days after the first assessment. Each site will make every effort to have these assessments at the Week 52 visit performed by the same study personnel who performed the assessments for the patient in the patisiran study in which they were previously enrolled.
- l One assessment of the NIS will be performed at each specified visit and must be performed by a neurologist.
- m Assessment of NIS only does not need to be repeated if done as part of the NIS+7 at the End of Study or Early Withdrawal visit or if done within the previous 26 weeks.
- n Grip strength will be measured in triplicate using a dynamometer held in the dominant hand. Every effort will be made to use the same device for a patient throughout the duration of the study. Two assessments of the grip strength will be performed on separate days (1 assessment on each day). The second (repeat) assessment must be conducted at least 24 hours (approximately) after the first assessment, but not more than 7 days apart.
- o Assessment does not need to be repeated if done within the previous 26 weeks.
- p The patient will be asked to walk 10 meters. The walk must be completed without assistance from another person; ambulatory aids such as canes and walkers are permitted. The time required for the patient to walk 10 meters will be recorded. Two assessments of the 10-meter walk test will be performed on separate days (1 assessment on each day). The second (repeat) assessment must be conducted at least 24 hours (approximately) but not more than 7 days after the first assessment.
- q Examination will include visual acuity, visual fields, and slit-lamp evaluation. An electroretinogram may also be performed, as described in Section 9.1.6.
- r Optional skin biopsies will only be obtained if the patient had skin biopsies in the parent study and has provided separate informed consent for the skin biopsies in this study. Each skin biopsy assessment will include 2 sets of tandem 3-mm skin punch biopsies (4 biopsies total), including 1 set of biopsies taken from the distal lower leg, when a patient's clinical status allows, and 1 set from the distal thigh.
- s Patients who are entering this study from a protocol that does not include the Norfolk QOL-DN questionnaire (eg, ALN-TTR02-003) do not have to complete this assessment.
- t Patients entering this study from study ALN-TTR02-003, who were not previously participating in the cardiac subgroup, will be required to have an echocardiogram before dosing on Day 0.
- u Serum samples for anti-drug antibodies will be collected as specified.
- v Patisiran will be administered once every 21 ( $\pm 3$ ) days. Every effort should be made to continue dosing from the parent study in the 21 ( $\pm 3$ ) day timeframe.

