### 3. INVESTIGATIONAL PLAN

#### 3.1. Overall Study Design

This is a multicenter, multinational, open-label extension study to evaluate the long-term safety and efficacy of patisiran in patients with FAP who have previously completed a patisiran study.

Consented eligible patients will enroll in this study and receive 0.3 mg/kg patisiran IV once every 21 days for the duration of the study. All dosing visits have a window of  $\pm 3$  days. In order to maintain the every 21-day dosing schedule from the parent study, patients are expected to have their first visit (Day 0) on this study 3 weeks after their last dose visit on the parent study. However, if necessary, a patient may initiate dosing in this study up to 45 days from the time of the last dose in the parent study. Exceptions to this timing may be allowed for medical or regulatory considerations only after consultation with the Medical Monitor. The last testing visit in the parent study will serve as the baseline for this study, unless more than 45 days have elapsed, in which case the baseline tests will need to be repeated on Day 0. Eligibility for this study will be confirmed before administration of the first dose on Day 0.

The duration of the study has been determined to allow the collection of long-term safety, tolerability and efficacy data of patisiran in patients with FAP who have completed a prior study with patisiran. The estimated duration of the study is 5 years.

In order to reduce the potential for an IRR with patisiran, all patients on this study will receive premedications at least 60 minutes before the start of the patisiran infusion. Patisiran will be administered as a 70-minute IV infusion (approximately 1 mL/minute for the first 15-minutes followed by approximately 3 mL/minute for the remainder of the infusion). If the infusion duration for a patient was lengthened beyond 70 minutes due to the occurrence of an IRR while on the parent study, that infusion duration may be continued on this study for that particular patient. Returning the patient's infusion duration to 70 minutes will require a discussion with the Medical Monitor.

After the Day 0 visit, patients should return to the clinical site for patisiran dosing once every 21 ( $\pm 3$ ) days. Patients will also have visits at the clinical site at approximately 12, 26 and 52 weeks, and yearly thereafter.

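### The 26-week waiver at the Early Withdrawal visit does not exclude the baseline, so patients who leave within about the first 20 to 26 weeks may have no post-baseline Norfolk QOL-DN, EQ-5D or FAP stage/PND score

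*Protocol*

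**What the plan says.** All references are to the protocol, Version 3.1 Brazil, unless stated otherwise.

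- **Schedule.** In Table 1 the rows for Norfolk QOL-DN, EQ-5D and "FAP Stage and PND Score" have entries at Day 0, Week 52, the annual visits, End of Study and Early Withdrawal. They have none at Week 12 or Week 26.
- **Waiver.** The Early Withdrawal entries in these rows carry footnote o: "Assessment does not need to be repeated if done within the previous 26 weeks".
- **Baseline.** The Day 0 entries carry footnote d: "Assessment/procedure does not need to be repeated if performed during the parent study within 45 days of first dose in this study". Section 3.1 agrees: "The last testing visit in the parent study will serve as the baseline for this study, unless more than 45 days have elapsed".
- **Timing of the visit.** The Early Withdrawal visit is set at "4 (+1) Weeks from Last Dose".
- **Other efficacy measures.** At Early Withdrawal, mNIS+7, NIS+7, grip strength, the 10-meter walk, COMPASS 31, the row "R-ODS Disability", the echocardiogram, the cardiac biomarkers and NYHA class carry footnote f instead: "Assessment/procedure required only if patient withdraws before the 52-week visit". That footnote has no 26-week look-back.

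**The concern.** A 26-week look-back makes sense when the earlier value is a recent on-treatment measurement. Here, for anyone who leaves in roughly the first half year, the only scheduled value inside the look-back is the baseline. Using it in place of the withdrawal assessment gives no information about change on treatment.

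The disease is progressive. Section 4.3 lists serious or intolerable adverse events and the need for a prohibited medication among the reasons for withdrawal. Section 5.2 bars tafamidis, diflunisal and doxycycline/TUDCA before the 52-week visit for patients who were not already taking them, so a patient who needs one because of worsening is a plausible early leaver. The missing values may therefore be informative.

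Section 10.2.3 plans changes from baseline for EQ-5D and for FAP stage and PND score, and Section 10.2.1 makes all enrolled patients the primary efficacy set. A patient with no post-baseline value contributes no change to those summaries. Because this is a rule about data collection, no analysis plan can repair it afterwards.

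**Working it through.** The protocol states no figure on this point, so there is none to reproduce. The check is calendar arithmetic plus a reading of the footnotes.

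**Inputs**
- Look-back: 26 weeks × 7 = 182 days (footnote o).
- Lag L from the baseline assessment to Day 0: 0 days if done on Day 0, up to 45 days if taken from the parent study (footnote d). L = 21 is an intermediate value chosen for illustration.
- Early Withdrawal visit: 28 to 35 days after the last dose (Table 1).
- Dosing interval: 21 days, first dose on Day 0.

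**Formulas**
- Latest Early Withdrawal day on which the baseline still satisfies footnote o = 182 − L.
- Corresponding latest last dose = (182 − L) − 35 to (182 − L) − 28.
- Nominal doses received by then = whole part of (day of last dose ÷ 21), plus 1.

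| L (days) | Latest Early Withdrawal day | Week | Latest last dose (day) | Nominal doses |
|---|---|---|---|---|
| 0 | 182 − 0 = 182 | 26.0 | 147–154 | 8 |
| 21 | 182 − 21 = 161 | 23.0 | 126–133 | 7 |
| 45 | 182 − 45 = 137 | 19.6 | 102–109 | 5–6 |

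A patient can thus receive between five and eight doses, attend the Early Withdrawal visit, follow the protocol exactly, and have only a baseline value on the three measures. Once the visit falls later than the day shown, the baseline is too old and the assessments are due.

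**Share of first-year withdrawals affected (illustration only).** The protocol gives no withdrawal rate. If Early Withdrawal visits were spread evenly over days 28 to 364, the share inside the window would be (182 − L − 28) ÷ (364 − 28):
- L = 0: 154 ÷ 336 = 46%
- L = 21: 133 ÷ 336 = 40%
- L = 45: 109 ÷ 336 = 32%

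**The two footnotes side by side.** Take a withdrawal visit at Week 18. Footnote f requires mNIS+7 and NIS+7, which footnotes j and k say are done twice on separate days, as well as R-ODS, COMPASS 31, grip strength and the walk test. Footnote o lets the site skip EQ-5D, Norfolk QOL-DN and the FAP stage/PND grade for the same patient. The protocol gives no reason for the difference, and burden does not explain it.

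**The case against.** The strongest reply is that early leavers are already well covered. Footnote f secures the core neuropathy, motor, autonomic and cardiac outcomes of anyone who withdraws before Week 52. Footnote o is permissive, so a site may still do the assessments. The study is descriptive, with no sample size based on hypothesis tests. Patients from ALN-TTR02-003 do not complete Norfolk QOL-DN in any case (footnote s). All of this stands and keeps the point small. It does not supply the values missing on the three measures, and a permissive rule leaves collection to each site.

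It could also be argued that a parent-study value was not done under this protocol and so cannot satisfy footnote o. The text does not say so, and an assessment done on Day 0 of this study would satisfy it on either reading.

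A reader might infer more than the protocol supports:
- **Disability in general is lost.** It is not. R-ODS, the patient-reported disability scale, is required before Week 52 under footnote f. Only FAP stage/PND is exposed.
- **Nutrition data are lost.** The mBMI row does carry footnote o. However, weight is taken before every dose, and albumin is part of the safety chemistry drawn at Weeks 12 and 26 and at Early Withdrawal without a waiver. Section 8.1.4 has mBMI calculated in the database, so the inputs for a post-baseline value exist.
- **NIS is lost or biased.** Before Week 52 the full NIS is obtained within the required NIS+7. The clause "or if done within the previous 26 weeks" in footnote m matters only after Week 52, when patients already have post-baseline data, and is a defensible trade-off against burden. Any estimate of bias in mean NIS would need a withdrawal rate that the protocol does not give and a last-available-value efficacy summary that it does not plan.

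**Conclusion.** The point holds for three measures and one window: Norfolk QOL-DN (where applicable), EQ-5D and FAP stage/PND score, at Early Withdrawal visits up to about study day 137 to 182, depending on the age of the baseline. For those visits footnote o, read literally, lets the baseline replace the withdrawal assessment, while footnote f requires comparable or heavier testing of the same patient.

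The window follows from the protocol's own figures. The lower end, day 137, assumes that a parent-study assessment counts under footnote o. The 32% to 46% share rests on an assumed even spread of visits and is not a forecast. How many patients are affected, and in which direction their missing values would move the summaries, cannot be determined from the protocol. This is a cheap improvement to data collection and does not threaten the study's main conclusions.

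**What to change.** In Table 1, for Norfolk QOL-DN, EQ-5D and FAP stage/PND score in the Early Withdrawal column, add to footnote o that only an assessment done after the first dose in this study satisfies the 26-week waiver. Because none of the three is scheduled between Day 0 and Week 52, they would then be required at any withdrawal before Week 52 (unless done at an unscheduled visit in the preceding 26 weeks), in line with footnote f. The window in which the baseline can stand in falls from 137–182 days to zero. The waiver can stay as it is for the other rows and for the End of Study visit.

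The same footnote wording appears in the Brazil 2.1, France and Germany 2.1 and Japan 2.2 versions. Make the same change in any other version in force that has it.

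Cost: a footnote amendment, plus two short questionnaires and a staging grade per early-withdrawing patient, at a visit already held.
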